A physician will evaluate each AE for severity, seriousness, and relationship to the MC procedure, per the categories and criteria delineated in the *AE Action Guide for Voluntary Medical Male Circumcision by Surgery or Device, 2nd Edition* (see Appendix XV for table of AEs and severity). To ensure objectivity, the evaluating physician will be brought in from a site other than where the circumcision was performed. Any evaluating physician should be trained in male circumcision, and have experience evaluating adverse events. Methods to assess the severity, seriousness and relatedness of the AE are detailed in the evaluation SOP manual. Evaluation physicians will be trained to make these assessments in a manner as standardized as possible. The site coordinator will verify that this information will be captured during every evaluation subject visit. AEs will be managed medically as appropriate, and will be followed until resolution or until a clinically stable endpoint is achieved.

The incidence and severity of all AEs related to the circumcision procedure will be documented and collected on the appropriate visit section and device-related events form of the CRF. This form will include a description of the onset, duration, relationship to the procedure, severity, seriousness, and final outcome of the AE. Severe and serious AEs, as well as AEs related to client self-removal of the ShangRing, will also be documented on the ShangRing Device Related Adverse Events form (see Appendix XIV), which must be completed for all AEs that result in hospitalization and all AEs classified as severe per the AE classification guidelines, as well as for those whose severity cannot be classified. The evaluation will compile and analyze mild, moderate and severe AE to determine the AE rate. All other device-related events, including expected side effects and occurrences resulting from clients' failure to follow instructions, will be compiled and summarized to inform program policy related to ShangRing use.

For the purposes of this evaluation, **all** severe AEs must be reported to the CDC **within 24 hours of notification**. Standard reporting procedures for all **notifiable** AEs must be followed per PEPFAR and national guidelines.

ShangRing and Tetanus

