Participation in this evaluation is believed to pose no more than minimal risks. Potential complications of the ShangRing device circumcision include excessive bleeding, hematoma, infection, pain, wound dehiscence, injury to the glans or urethra, excessive or insufficient skin removal, and poor cosmetic results. The use of the ShangRing device has yielded low rates of adverse events in different studies. In a proof of concept evaluation in Kenya, all 40 procedures were completed successfully.³⁴ Only three mild adverse events, all cutaneous injuries of the skin of the penis, was reported among the 40 clients (7.5%) and mean pain scores were low. A second evaluation in Kenya enrolled 197 men, each of whom received successful ShangRing circumcisions, these were compared against 201 men who received conventional surgical circumcisions.³⁵ The ShangRing group experienced AEs at a similar rate to the conventional surgical circumcision group, with 14 moderate and one severe AE in the ShangRing group (7.6%) and 10 moderate AEs in the conventional surgical circumcision group (5.0%). The severe AE was a case of pain that occurred in the ShangRing group during the circumcision. The other AEs included: wound dehiscence, post-procedure pain, and an anesthetic complication. All AEs were

treated and resolved without problems. The pain scores between the two groups were similar at most points of time, with the exception that the pain during an erection while the device is in place was significantly higher for the ShangRing group. A comparative evaluation in Uganda found that a majority of men chose ShangRing over the dorsal slit method when asked to choose a preferred procedure, 508 chose ShangRing compared to 113 (though four men who chose ShangRing had to receive conventional circumcision when the ShangRing procedure failed, these failures occurred early in the evaluation and were attributed to provider inexperience).³⁶ There were no differences in the rate of moderate and severe AEs between the two groups – five total (1%) in the ShangRing group, and one (.9%) in the conventional surgical circumcision group. The AEs included post-operative pain, bleeding, infection, wound dehiscence, and insufficient skin removal. Additional studies in Kenya and Zambia have found similar rates of AEs between ShangRing procedures and conventional circumcision.³⁷

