Client is eligible for ShangRing circumcision (circle one)? Yes No If No, Specify Reason: _____

Confirmation of client's eligibility (circle one):

1. In good health: Yes No
2. Counseled: Yes No
3. Consented: Yes No N/A (13-17 years old)
4. If 13-17 year-old client, consent by parent/guardian and assent by client: Yes No N/A

If 'No' for any of the above, explain: _____

Part 2 – ShangRing Device Placement Procedure

Device size: _____ Expiration Date (dd-mm-yyyy): _____

If the device application is not the same day as the screening report, has there been a change in the genitals (compare to screening visit report)? Yes No

Time placement procedure began (e.g. 14:30): _____

Time placement procedure ended (e.g. 14:45): _____

Comments: _____

Was the device applied according to its Instructions for Use (circle one)? Yes No

If "No," explain in detail: _____

Was the penis disinfected before applying the device (circle one): Yes No

What form of anesthesia was used? Indicate injection/cream, what kind for each, and for injection provide dosage: _____

Please Attach ShangRing Label Here:

Was there an Adverse Event during placement (circle one)? Yes No

If yes, how would you rate the AE (circle one, refer to definitions below): Mild Moderate Severe

Severity cannot be classified (if problem with placement or device malfunction)

Adverse Event Definitions:

Mild: classification indicates minimal or no intervention is required beyond reassurance and observation

Moderate: classification relates to those AEs that are neither mild nor severe, require intervention, and are usually managed on site

Severe: classification requires extensive intervention with referral or specialist input

NB: If any Moderate, Severe, or Severity not classified adverse events above are checked, complete the AE form.

Full name and surname of clinician placing device: _____

Signature: _____ Cadre (e.g. physician, nurse): _____

Full name and surname of assistant: _____

Signature: _____ Cadre (e.g. physician, nurse): _____

Part 3 – Post-Application Evaluation and Assessment (Before Discharge)

Dressing intact and holding penis against abdomen (circle one)? Yes No

Client given post-procedure written instructions (circle one)? Yes No

Clinical disposition of client, including AE management: _____

Oral analgesia given (circle one)? Yes No Drug (name, dose, quantity dispensed): _____

Scheduled removal date (dd-mm-yyyy): _____

Discharged by (Full name and surname): _____

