Was client reminded to return to the site in the event of any unexpected situation, in case of pain, or if client has not yet had ring removed, if ring is displaced (select one)? Yes No

Adverse Events

Was there an Adverse Event seen/reported during follow-up (select one): Yes No

If yes, how would you rate the AE (circle one, refer to definitions below): Mild Moderate Severe

Severity cannot be classified (if problem with placement)

Adverse Event Definitions:

Mild: classification indicates minimal or no intervention is required beyond reassurance and observation

Moderate: classification relates to those AEs that are neither mild nor severe, require intervention, and are usually managed on site

Severe: classification requires extensive intervention with referral or specialist input

NB: If any Moderate, Severe, or Severity not classified adverse events above are checked, complete the AE form.

For unscheduled visits, has the client experienced a device-related event or AE since his last visit (select one):

Yes No NA (not an unscheduled visit)

For unscheduled visits, please describe the reason for the unscheduled visit: _____

Is circumcision progressing as expected (select one)? Yes No

If "No," please explain: _____

Assessment (Before Discharge)

Clinical disposition and AE management: _____

Next visit date, if applicable (dd-mm-yyyy): _____

Discharged by (Full name and surname): _____

Signature: _____

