Appendix XVIII – Adverse Event Reporting Form

Client ID:

Device Related Events Form

Has the participant experienced a device related event per protocol? This includes mild, moderate and severe AE, expected side effects such as common post-operative findings, occurrences resulting from participants' failure to follow instructions, and device malfunctions. Please consult the *Adverse Event Classifications and Definitions: During Device Placement or Wearing and During or After Device Removal* for clarification and definition of adverse events. If the client is determined to have experienced an adverse event, please complete below.

If this is an AE defined as moderate or severe, also fill in the corresponding AE form. Note, that notifiable adverse events must also be reported also per PEPFAR and national guidelines.

Client ID:

Device Events Form

Device Event (Indicate type)	Evaluation Phase	Start/Onset
 Anesthetic Related Problem	During placement  While in place  (before discharge)	Date:
 Bleeding	During removal  After removal 	Time:
 Pain		
 Scarring/Disfigurement Poor cosmetic result or excess skin removal	Severity (Consult definitions for grading classification)	Events/AE Code (Consult definitions for codes)
	Mild 	
	Moderate 	
	Severe 	
 Device Displacement	Moderate or Severe AE	Relationship to Device
 Device detachment	Yes  No 	Unrelated 
 Infection	If "Yes," complete adverse events form	Possibly 
 Injury to penis		Definitely 
 Sexual effects/ undesirable sensory changes		
 Wound Disruption	Action	Pain VAS (see below)
 Excess swelling of penis/scrotum	None  Pharmaceutical 	
 Hematoma	Surgical  Non-surgical 	
 Difficulty with removal	Evaluation termination 	

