 Difficulty urinating	Other  Specify: _____	
 Excessive skin removal		
 Other		
	Complete when resolved or at final visit	
	Outcome	End/Termination
	Resolved  Resolved with sequel 	Date:
	Persistent  Unchanged 	Time:
	Unknown 	

Visual Analog Scale (VAS):

I have checked all data introduced to this form until this point and verified that they are complete, correct and reconcilable with the original documentation.

Evaluation Coordinator's Signature: _____

Date: _____

Client ID:

Adverse Events (AE) Form

Has the participant experienced a moderate or severe AE per protocol? If "No", do not enter information on this form. If the AE is defined as severe, notify the principal investigators based on the evaluation protocol.

Adverse Event	Start/Onset	Status	Device Event Number
	Date: Time: Date/time observed (if different):	New  Ongoing 	
	Action	Severity (Consult definitions for grading classification)	AE Code (Consult definitions for codes)
	None  Pharmaceutical  Surgical  Non-surgical  Evaluation termination  Other  Specify: _____	Moderate  Severe  If severe, complete information below	
	Date of SAE report to evaluation investigators:	Was the SAE a result of protocol departure? Yes  No  If "Yes," please specify:	
	Date of last visit and last visit number:	Date the device was applied:	
	Please describe the SAE in block letters (use following page if additional space is needed):	Choose criteria for SAE:  Death  Permanent disability  Life threatening  Hospitalization or prolongation of inpatient hospitalization  Required intervention to prevent one of the above  Other: _____	
	Outcome	End/Termination	
	Resolved  Resolved with sequel  Persistent  Unchanged  Unknown 	Date: Time:	

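### Events rated as not classifiable for severity are routed to an AE form that does not admit them, and the protocol conflicts on whether they count in the primary AE rate

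*Protocol*

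**What the plan says.** **Ratings on the CRFs.** Part 2 of the placement CRF (Appendix IX) gives a fourth option beside mild, moderate and severe: "Severity cannot be classified (if problem with placement or device malfunction". The follow-up CRF (Appendix XII), used at removal and unscheduled visits, words it "Severity cannot be classified (if problem with placement" and leaves malfunction out. Both carry the same routing note: "If any Moderate, Severe, or Severity not classified adverse events above are checked, complete the AE form".

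**Body text.** The section on AE and device-related incident documentation requires a form for severe and serious AEs and certain others, "as well as for those whose severity cannot be classified".

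**The receiving forms (Appendix XVIII).** The AE form opens with "Has the participant experienced a moderate or severe AE per protocol" and, if the answer is no, says "do not enter information on this form". Its severity boxes are Moderate and Severe. The Device Related Events Form is wider in scope and covers "occurrences resulting from participants' failure to follow instructions, and device malfunctions", but its severity boxes are Mild, Moderate and Severe, and it passes only moderate or severe AEs on to the AE form.

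**The rate.** The AE documentation section takes the AE rate from mild, moderate and severe AEs and has other device-related events compiled and summarised. The primary endpoint, in the Executive Summary and in the Primary Endpoint section, takes in all device-related malfunctions. The Analysis Overview defines the rate as the percentage of clients with at least one AE and sets no condition on grade.

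**The concern.** The protocol creates a rating for problems that do not fit the severity scale, chiefly placement problems and device malfunctions, and then gives it no consistent route. Two CRF notes and the body text require a form for such an event, the AE form the CRFs point to does not admit it, and the other form has no matching grade.

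This reaches the primary endpoint because the numerator is governed by two rules that differ on exactly these events. An analyst following the AE documentation section would leave an ungraded malfunction out of the rate and describe it separately. An analyst following the primary endpoint text would count it. The Analysis Overview does not settle whether an ungraded event is an AE. The same data could therefore yield two primary results. Leaving the events out can only lower the rate, and the events at issue are failures specific to the device under evaluation.

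**Working it through.** **1. The routing, side by side.**

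| Place | Admits an unclassified event? |
|---|---|
| Placement CRF, Appendix IX | Yes, for a placement problem or malfunction; sends it to the AE form |
| Follow-up CRF, Appendix XII | Yes, for a placement problem only; sends it to the AE form |
| AE documentation section | Yes, requires a form |
| AE form, Appendix XVIII | No, moderate or severe only |
| Device Related Events Form, Appendix XVIII | Records the event, but has no unclassified grade |

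**2. The numerator, side by side.** Take a client whose only event is a malfunction that stays ungraded.
- Primary endpoint text: counted, because all malfunctions are included.
- AE documentation section: not counted, only summarised.
- Analysis Overview: counted if the event is treated as an AE, which is not stated.

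**3. The plan's own precision figure.** The sample size section gives 335 for 95% confidence, a margin of 1.5 points and a 2% rate.
- n = z² p(1 − p) / h² = 1.96² × 0.02 × 0.98 / 0.015² = 334.6, rounded up to 335. It reproduces.
- At the full sample of 575 the half-width is 1.96 × √(0.02 × 0.98 / 575) = 1.14 points.

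**4. What omission could do.** The protocol gives no expected number of ungraded clients, so that number, u, is assumed. Start from 12 clients with a graded AE among 575 (about 2%) and add u clients whose only event is ungraded. Rate = (12 + u) / 575, with exact (Clopper-Pearson) 95% intervals.

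| u | Clients counted | Rate | 95% interval |
|---|---|---|---|
| 0 | 12 | 2.09% | 1.08 to 3.62% |
| 2 | 14 | 2.43% | 1.34 to 4.05% |
| 5 | 17 | 2.96% | 1.73 to 4.69% |
| 10 | 22 | 3.83% | 2.41 to 5.74% |

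At u = 5 the two counting rules differ by 5 / 575 = 0.87 points, about three quarters of the 1.14-point half-width (0.87 / 1.14 = 0.76). The upper limit, which the Analysis Overview singles out for reporting, moves from 3.62% to 4.69%.

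**5. Where u = 5 comes from.** The section on potential harm describes a Uganda comparison in which 508 men chose the device and "four men who chose ShangRing had to receive conventional circumcision when the ShangRing procedure failed". That is 4 / 508 = 0.79%, or 575 × 4 / 508 = 4.5 clients. It is the only failed-placement share in the protocol and sets a scale for the illustration; it is not a forecast.

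**The case against.** A reader might infer that failed placements and malfunctions disappear from the data, or certainly from the rate. The documents do not support that.

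- The event is already on the CRF, as an AE with the unclassified rating, before anyone reaches the AE form. The body text also requires all events, malfunctions included, on the device-related events form, which has an *Other* box.
- A physician from another site is to evaluate each AE for severity, so an event left ungraded at the visit may be graded later. Appendix XIX has a row for other AEs, and the Primary Endpoint section gives general severity definitions that could be applied.
- Self-removal is not homeless: Appendix XIX grades it as moderate or severe under Device Displacement, which is a box on the Device Related Events Form.
- Staff are not forced to choose between an invented grade and silence. The CRF instructions allow an entry for unknown data.
- The missing malfunction wording on the follow-up CRF has limited effect, since that form separately asks about device-related events at removal and at unscheduled visits.

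These points stand, and they reduce the consequence from a demonstrated loss to a risk. They do not remove the conflict. An entry for unknown data is not the rating that the CRF created. The physician works from a table with no named row for malfunction, and nothing says that every unclassified event must leave review with a grade. For any event that stays ungraded, the two counting rules still disagree.

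A reader might also take 0.8 points as the expected bias. That is not supported either. The protocol says the four Uganda failures came early and were put down to provider inexperience, whereas providers here complete at least 10 placements in training. Nor does it say whether the 2% planning rate includes failed placements.

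**Conclusion.** The protocol contradicts itself on two linked points: whether an event of unclassifiable severity may be entered on the AE form, and whether a client whose only event is ungraded counts in the primary AE rate. Both stand on the text alone.

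The effect on the rate is a one-directional risk of under-counting and cannot be sized from the documents. The shift of 0.87 points assumes 12 clients with graded AEs, 5 further clients with only ungraded events, no later grading of those 5, and a denominator of 575. With 2 such clients the shift is 2 / 575 = 0.35 points; with none it is zero. The correction is worth making because the endpoint names malfunctions explicitly and the change costs very little.

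**What to change.** 1. In Appendix XVIII, add the unclassified rating to the severity item on both the Device Related Events Form and the AE form.
2. Change the AE form's entry question so that it admits moderate, severe or not classifiable events, matching the CRF routing note.
3. In Appendix XII, restore device malfunction to the fourth rating so that it agrees with Appendix IX.
4. Reconcile the rate rule in the AE documentation section with the primary endpoint and the Analysis Overview: state that a client with an unclassified event or a device malfunction counts in the primary AE numerator, and that these clients are also shown separately.

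Separate tick boxes for self-removal or malfunction are optional, since Device Displacement and *Other* already cover them. The cost is a few form edits and a sentence in the text; the reported AE rate may come out slightly higher.

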Appendix XIII – Introductory script for contacting ShangRing clients by phone

Introductory script for contacting ShangRing clients by phone

May I please speak to _____?

If yes, proceed to next paragraph

If no, is there better time to call you later? If yes, schedule appointment follow another call

My name is _____ and I am calling from _____ (*name of health facility*) to follow up on your appointment to visit our clinic on _____ (*date*) for _____ (*purpose of missed appointment*). At your last visit to our clinic you indicated that you would come for _____ (*purpose of missed visit e.g. review or device removal*). May I ask if you may be available for this appointment at a different time?

Schedule another appointment for clinic visit or for home visit by providers depending on his availability.

If the client is not at home, but another person answers the phone, a message will not be left for the person who answers the phone. Proceed as follows;

My name is _____.

May I know when he is likely to be back for me to call him on this same number or can you guide me on how else I can reach him?

Depending on the response, schedule another call or follow guidance given on how to reach him.

Appendix XIV – ShangRing Adverse Event Day 3 Post-Removal AE Check-in Call Form

ShangRing Adverse Event Check-in Call Form

Client ID:

Instructions

This form is to be used during the call with clients to check for signs of adverse events three days following the removal of the ShangRing device. The questions below are meant to evaluate whether the client is potentially experiencing an adverse event in the aftermath of their circumcision. After introducing yourself, and informing the client of the purpose of the call, ask the client each question on the list. For any 'yes' answers, probe for more information. If any of the information the client offers suggests an adverse event, advise that the client come to the clinic immediately for further evaluation.

Questions

1. Are you experiencing pain that keeps you from doing anything you normally do? **Y** **N**

a. **If yes:** Advise the client to visit the clinic to be evaluated

Note any comments: _____

2. Has swelling, tenderness or pain around the wound gotten worse since your circumcision? **Y** **N**

a. **If yes:** Advise the client to visit the clinic to be evaluated

Note any comments: _____

3. Have you noticed any expanding redness around the wound area, or red streaking spreading from the wound? **Y** **N**

a. **If yes:** Advise the client to visit the clinic to be evaluated

Note any comments: _____

4. Have you noticed any pus or fluid coming from the wound area? **Y** **N**

a. **If yes:** Advise the client to visit the clinic to be evaluated

Note any comments: _____

5. Have you felt like you have had a fever in the past few days, or experienced chills, shaking, breaking into sweats more than usual? **Y** **N**

a. **If yes:** Advise the client to visit the clinic to be evaluated

Note any comments: _____

6. Are you still bleeding from the wound area? **Y N**

a. **If yes:** Advise the client to visit the clinic to be evaluated

Note any comments: _____

7. Are you experiencing any difficulty urinating? **Y N**

a. **If yes:** Advise the client to visit the clinic to be evaluated

Note any comments: _____

8. Are you experiencing any other new problems since the surgery? **Y N**

a. **If yes:** Ask the client to describe the symptoms, and record below. If the symptoms are concerning advise the client to visit the clinic to be evaluated.

Note any comments: _____

Upon conclusion, thank the client for their time and remind them of their visit for the healing assessment in 39 days' time. If the client is one of those selected to participate in the qualitative interview, remind them of the date of the interview.

